3.2. Treatment Groups and Duration

Subjects entering with a PGA ≥ 1 will receive treatment with tapinarof cream, 1% until they achieve a PGA score of 0, at which time treatment will be discontinued and subjects monitored for durability of response. If or when disease worsening occurs, as evidenced by a PGA ≥ 2 , treatment will then be re-initiated and continued until a PGA of 0 is observed. Subjects entering with a PGA of 0 will have treatment discontinued and be monitored for durability of response. If/when disease worsening occurs, as evidenced by a PGA ≥ 2 , treatment will then be re-initiated and continued until a PGA of 0 is observed. (Section [5.1.5.2](#)).

A subject will be considered to have completed the study when he/she completes all required procedures/visits for the 40-week (Visit 11) treatment period. The end of the study is defined as when the last active subject has completed the Follow-up Visit.

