6.3. Safety Assessments

6.3.1. Adverse Events

All AEs will be collected from the time the subject signs the ICF until the final visit/contact with the subject. Adverse events that began during the pivotal study and were ongoing at the end of that study will be reported as ongoing AEs. Additional safety information, including the definition of an AE and the methods for recording, evaluating, and assessing causality of AEs and the procedures for completing and transmitting SAE reports are provided in Section 8.

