7.8. End of Study

The end of the study is defined as when the last active subject has completed the Follow-up Visit (Week 44).

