8.3. Time Period and Frequency for Event Assessment and Follow-up

8.3.1. Adverse Event Reporting

All AEs will be collected from the time of signed informed consent until the final visit.

Any AEs assessed as related to study participation (e.g., protocol-mandated procedures, invasive tests, or change in existing therapy) will be collected from the time a subject consented to participate in the study up to and including any follow-up contact.

All SAEs will be recorded in the eCRF and reported to the Sponsor within 24 hours via email or phone (refer to Medical Monitor/Sponsor Information page for contact information) (see Section 8.4).

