10.4.3. Safety Analyses

The number and percent of subjects with TEAEs will be summarized by system organ class and preferred term for all TEAEs, all TEAEs considered by the Investigator to be related to study drug, all SAEs, and all TEAEs leading to study drug discontinuation. All adverse event summaries will include information for adverse events that occurred after administration of the first dose of study drug until completion of the final study visit. Data listings will be provided for subjects who discontinued the study due to an adverse event and for subjects with an SAE.

Selected clinical laboratory data will be analyzed using descriptive summary statistics, including the number of nonmissing observations, mean and SD, median, upper and lower quartiles, minimum and maximum for values and changes from Baseline. Categorical safety data will be analyzed using frequency tables and, if applicable, shift tables.

Vital signs will be listed by subject and summarized by visit.

Mean scores from the LTS will be summarized by visit.

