A subject is considered to have completed the study when he/she completes all required procedures/visits for the 40-week (Visit 11) treatment period. The end of the study is defined as when the last active subject has completed the Follow-up Visit.

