- Age (<65 and \geq 65 years old)
- Sex
- Race (White, Other)

Furthermore, TEAEs will be categorized by day of onset among the following 4 categories:

- \leq 12 weeks
- >12 to \leq 24 weeks
- >24 to \leq 40 weeks
- >40 weeks.

For each of these categories, TEAEs will be summarized by SOC in alphabetical order and PT in descending order of frequency. TEAEs ongoing at the end of the pivotal studies will be considered in the first category (i.e. day of onset \leq 12 weeks).

At each level of summarization, a subject will be counted once if he/she reported one or more events. The severity of TEAEs and relationship to study drug will be summarized in a similar

manner. For summaries of relationship to study drug, a subject will be classified according to the closest relationship. For summaries of TEAE CTCAE grade, a subject will be classified according to the worst grade.

For AESIs, summarization will be more extensive, reflecting the more detailed information collected. Information summarized will include number of events per subject, earliest onset day, duration (in days), causality, grade and seriousness of AESIs, outcome, actions taken, assorted physical characteristics of the AESIs, and demographic/baseline characteristics and PGA status of the subjects experiencing them. Each type of AESI will be summarized separately. If a subject has more than one treatment-emergent occurrence of an AESI, the subject's maximum duration, highest levels of causality and seriousness, maximum grade and generally the most extreme level of each characteristic will be summarized. If an AESI was ongoing at end of study (EOS), it will not be included in the duration summary. AESIs ongoing at the end of pivotal studies will also be included in the summary.

A Kaplan-Meier figure will be generated for each AESI of time to first event for events starting during the study. Subjects not experiencing the AESI will be censored at the date of study completion or discontinuation. AESIs ongoing at the end of pivotal studies will not be included.

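### The AESI Kaplan-Meier figures count first events up to the follow-up visit but, read by the documents' own definition of completion, censor event-free completers at Week 40, which biases the tail upward

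*SAP*

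**What the plan says.** **Events.** SAP 11.11.1: "A Kaplan-Meier figure will be generated for each AESI of time to first event for events starting during the study". No upper time limit is given. AESIs already ongoing when the pivotal study ended are left out.

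**Censoring.** The next sentence of the same section: "Subjects not experiencing the AESI will be censored at the date of study completion or discontinuation".

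**Completion of a subject.** SAP 3: "A subject is considered to have completed the study when he/she completes all required procedures/visits for the 40-week (Visit 11) treatment period". Protocol 3.2 has the same definition. In both documents the follow-up visit marks the end of the trial as a whole (also Protocol 7.8), not a subject's completion.

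**AE collection.** Protocol 6.3.1: "All AEs will be collected from the time the subject signs the ICF until the final visit/contact with the subject". Protocol 8.3.1 agrees, and Protocol 7.4 lists AE recording at the follow-up visit. Protocol 10.4.3 runs the AE summaries "until completion of the final study visit". SAP 11.11.1 treats every AE reported in this study as treatment-emergent, apart from pivotal-study events that resolved before Visit 1, and it has an onset category for events after Week 40. The plan therefore expects onsets in the follow-up period.

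**The concern.** Kaplan-Meier estimation requires that leaving the risk set be unrelated to the event. Here, events are counted to about Week 44 and event-free follow-up only to Week 40. A completer with a first folliculitis at Week 42 is kept at risk for two more weeks and counted as an event. A completer seen at Week 44 without folliculitis is removed at Week 40. After the Week 40 visits, the risk set therefore consists mainly of subjects who go on to have the event.

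The figures concern the three named AESIs (contact dermatitis, folliculitis, headache) in a study whose first-listed objective is safety and tolerability. A curve that jumps at its end would disagree with the AESI incidence tables in the same report.

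**Working it through.** **Inputs from the documents**
- 850 enrolled and about 300 completers (SAP 6).
- Visits every 4 weeks ±3 days (SAP 3), with Day 1 = Visit 1 (SAP 10.3).

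**Assumptions (the documents give no AESI rates)**
- 25 first AESIs before Week 40.
- Early exits spread evenly to Week 40.
- k first AESIs after Day 284.
- m event-free subjects with late Week 40 visits, still at risk through those events.

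**Step 1: days.** Study day = 7 × week + 1. Week 44 gives 7 × 44 + 1 = 309, the day shown in Protocol Table 1. Week 40 gives 7 × 40 + 1 = 281, so in-window Week 40 visits fall on Days 278–284 and follow-up visits on Days 306–312.

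**Step 2: estimate just before the tail.** S(t) is the product of (1 − d/n) over event times. Over 500 simulated cohorts on these inputs, cumulative incidence by Day 284 averaged 4.6% (range 4.0% to 5.5%), so S40 ≈ 0.9536.

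**Step 3: the tail as written.** Only m + k subjects remain at risk, and the factors telescope:

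S_end = S40 × (m+k−1)/(m+k) × … × m/(m+1) = S40 × m/(m+k)

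**Step 4: the tail with event-free completers censored at follow-up.** About 300 are at risk:

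S_end = S40 × (300−k)/300

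**Step 5: one late event (k = 1).**

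| Event-free subjects still at risk | As written, 1 − S_end | Censored at follow-up |
|---|---|---|
| m = 0 | 1 − 0.9536 × 0 = 100% | 1 − 0.9536 × 299/300 = 5.0% |
| m = 1 | 1 − 0.9536 × 1/2 = 52% | 5.0% |
| m = 5 | 1 − 0.9536 × 5/6 = 21% | 5.0% |
| m = 15 | 1 − 0.9536 × 15/16 = 11% | 5.0% |

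With three late events and m = 5, the curve as written ends at 1 − 0.9536 × 5/8 = 40%, against 1 − 0.9536 × 297/300 = 5.6% when censored at follow-up.

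**Step 6: sensitivity to the AESI rate.** One late event, with 2%, 5%, 10% or 20% of the 850 having a first AESI before Week 40:

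| Incidence by Day 284 | m = 0 | m = 1 | m = 5 | m = 15 | Censored at follow-up |
|---|---|---|---|---|---|
| 3.2% | 100% | 51.6% | 19.3% | 9.2% | 3.5% |
| 7.4% | 100% | 53.7% | 22.9% | 13.2% | 7.7% |
| 14.6% | 100% | 57.3% | 28.8% | 19.9% | 14.8% |
| 28.0% | 100% | 64.0% | 40.0% | 32.5% | 28.3% |

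With matched censoring, one late event adds 0.2 to 0.3 percentage points. As written, the jump depends mainly on how many Week 40 visits happened to run late.

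**The case against.** **Completion may be dated at follow-up.** The definition in both documents says when a subject counts as a completer; it does not say which date is recorded. SAP 3 gives participation as about 44 weeks, and SAP 11.1 falls back on the last visit date when the completion date is missing. SAP 9 and Protocol 10.5 tie study completion to the last subject's last visit. If the case report form dates completion at the follow-up visit, the mismatch is gone. That possibility stands, and the form is not among the documents. But SAP 9, Protocol 10.5 and the financial-disclosure wording in Protocol 11.1.1 speak of the trial, and a fallback for missing dates does not redefine the term. The only subject-level text points to Visit 11.

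**100% is a worst case.** This stands. A reader might infer that any late AESI takes the curve to 100%. It does so only if no event-free subject is still at risk at the last event. SAP 11.12 expects visits altered or missed because of COVID-19, so some late Week 40 visits are likely. They reduce the jump without removing the bias.

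**Not every completer is observed to Week 44.** This also stands. Protocol 7.4 times the follow-up visit from last treatment, some subjects may already be off drug at Week 40, and attendance is not assured. The right end point is each subject's own last AE contact, not a fixed Week 44.

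**The figures are descriptive.** SAP 10.1 rules out statistical testing, and a jump from a tiny risk set would be conspicuous. This limits the severity, but does not make the estimate correct.

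**Conclusion.** Wrong as written, low-to-moderate severity. On the only subject-level definition of completion that the documents give, the tail of each AESI curve after about Day 284 is biased upward. For one late event in the illustrated cohort, it ends anywhere from about 11% (15 late visits) to 100% (none), where about 5% is right. The AESI counts and the numbers of late visits are assumptions; the direction of the bias does not depend on them.

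The error does not arise if no first AESI begins after Week 40, or if the recorded completion date is the follow-up date. A late first AESI is nonetheless plausible: Protocol 1.3.1.2 lists headache among the most frequent nondermatological events.

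Two wider inferences are not supported. The AESI incidence tables, the onset-category tables and the curves up to Week 40 do not use this censoring rule in a way that distorts them. The days-in-study figure in SAP 11.1 measures time to the completion or discontinuation date itself, so it has no mismatch between events and censoring.

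**What to change.** In SAP 11.11.1, replace the censoring sentence with one of two rules:

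1. Censor subjects without the AESI at their last visit or contact at which AEs were collected: the follow-up visit if attended, otherwise the last earlier visit or contact. This uses all the AE data, and it also covers early discontinuers whose AEs are recorded after the discontinuation date.
2. Alternatively, end the figure at each completer's Visit 11 date, for events and censoring alike, and leave later onsets to the tables.

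If the recorded completion date is already the follow-up date, say so in the same sentence. SAP 11.1 needs no change. The cost is one sentence and a small change to the derivation of the censoring date. The visit dates are already recorded, so no new data are needed.

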11.11.2 Local Tolerability Scale (LTS)

LTS scores will be summarized by visit and DB treatment group for subject overall assessment (scores from 0=None to 4=Strong/Severe) and Investigator overall assessment (scores from 0=No irritation to 4=Very Severe) separately. LTS scores at the sensitive areas will be summarized by visit, area and DB treatment group for Investigator overall assessment as well as listed in a by-subject and by anatomical site listing.

11.11.3 Clinical Laboratory Testing

All clinical laboratory (hematology, clinical chemistry, urinalysis) values will be listed by DB treatment group and subject. The reference normal ranges and reference range indicators (e.g. high, low, normal etc.) will be supplied by the central laboratory and displayed in the data listings. For the purpose of shift table summaries, the central lab reported reference range indicators will be classified as low, normal and high accordingly based on the table below.

Reference Range Indicator in Shift Tables	Reference Range Indicator Reported by Central Lab
Low	Low, Low Level 1 Alert, Low Level 2 Alert
Normal	Normal
High	High, High Level 1 Alert, High Level 2 Alert

Values outside the normal range will be flagged. Change from baseline in abnormality status will be summarized using shift tables. For urinalysis, only lab tests with numeric results reported are included in shift tables. Separate listings will identify subjects with markedly abnormal values. For quantitative measures, observed values and change from baseline in clinical laboratory values will be summarized descriptively by visit, overall and by DB treatment group.

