2. OBJECTIVES AND ENDPOINTS

The objectives and associated endpoints of this study are as follows:

Objectives	Associated Endpoints

 To evaluate the safety and tolerability of tapinarof cream, 1% in adults with plaque psoriasis 	
 Incidence, frequency, and nature of AEs and SAEs Change over time in clinical laboratory tests and frequency of clinically significant abnormal test results Change over time in vital signs and frequency of clinically significant abnormal results [REDACTED]

 To describe the efficacy of tapinarof cream, 1% over an extended period of time in adults with plaque psoriasis 	
 Proportion of subjects who experience a PGA ≥ 2 at least 1 time in the study and the median time from baseline to first worsening (PGA ≥ 2) for subjects entering the study with a PGA score of clear (0) Proportion of subjects who achieve a PGA score of 0 at least 1 time in the study [REDACTED] Duration of each treatment episode, defined as time from each treatment initiation/re-initiation to each subsequent treatment success (PGA score of 0). [REDACTED] Proportion of subjects who never achieve a PGA ≥ 2 throughout the study Proportion of subjects who never achieve a PGA score of 0 or 1 throughout the study [REDACTED] [REDACTED] Change and percent change from baseline in %BSA affected by visit (OC and LOCF) Change and percent change in PASI score by visit (OC and LOCF) [REDACTED]

 To describe the effect of tapinarof cream, 1% on psoriasis symptom severity and the associated impact on daily activities and attitudes in adults with plaque psoriasis 	
 Change in disease impact on daily activities, as measured by the Dermatology Life Quality Index (DLQI) total and individual dimension scores

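### The laboratory tables described in SAP 11.11.3 give no count of subjects with important abnormalities, and the three-level shift tables do not show same-direction worsening from an abnormal baseline

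*SAP*

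**What the plan says.** The protocol's first objective is safety and tolerability. One of its endpoints (protocol section 2) is "Change over time in clinical laboratory tests and frequency of clinically significant abnormal test results".

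SAP 11.11.3 plans the following for laboratory data:

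- **Shift tables.** "Change from baseline in abnormality status will be summarized using shift tables". For these, "the central lab reported reference range indicators will be classified as low, normal and high accordingly based on the table below". The mapping puts "Low, Low Level 1 Alert, Low Level 2 Alert" into Low and "High, High Level 1 Alert, High Level 2 Alert" into High.
- **Descriptive statistics.** "For quantitative measures, observed values and change from baseline in clinical laboratory values will be summarized descriptively by visit, overall and by DB treatment group". Under SAP 10.1 these statistics include the minimum and maximum; protocol 10.4.3 also plans quartiles.
- **Listings.** The reference ranges and the laboratory's own indicators "will be supplied by the central laboratory and displayed in the data listings". In addition, "Separate listings will identify subjects with markedly abnormal values". The section does not say what makes a laboratory value markedly abnormal.

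For vital signs, SAP 11.11.4 sets numerical limits for a markedly abnormal change in blood pressure and pulse. Subjects who meet them are to be both flagged in a listing and counted in a table.

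**The concern.** The central laboratory supplies a graded indicator, and the shift table uses only its direction. A subject who is High at baseline and reaches a Level 2 alert later is tabulated as High to High. A subject who goes from Normal to a Level 2 alert shares a cell with one who goes from Normal to just above the range. With markedly abnormal values sent only to listings, no laboratory table described in the text says how many subjects had an important abnormality.

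This matters because the study is open-label with no concurrent control, plans no statistical testing (SAP 10.1) and has no independent data monitoring committee (protocol 8.6). The descriptive counts are the evidence. Protocol 1.3.1.2 cites nonclinical liver and thymus findings, with secondary hematological findings, and names laboratory monitoring among the mitigations. A count of subjects reaching an alert level would summarize that monitoring directly.

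**Working it through.** No sample size, power or event figure bears on this point, and the plan gives no figure of its own to reproduce. The check is to enumerate the mapping in SAP 11.11.3 and then see what else in the two documents could supply the count.

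**Step 1: inputs.** The laboratory reports seven levels: Low Level 2, Low Level 1, Low, Normal, High, High Level 1, High Level 2. The SAP maps them to three: Low, Normal, High.

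**Step 2: same-direction worsening.** Each side has four ordered levels (Normal, plain abnormal, Level 1, Level 2). A worsening is any move to a more extreme level on that side: 4 × 3 / 2 = 6 per side, so 2 × 6 = 12 in all. Those that start and end within the three abnormal levels stay in one shift-table cell: 3 × 2 / 2 = 3 per side, so 2 × 3 = 6.

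| Transition type (both sides together) | Number | Shown as a shift? |
|---|---|---|
| Normal to plain High or Low | 2 | Yes |
| Normal to a Level 1 or Level 2 alert | 4 | Yes, pooled with the row above |
| Plain High or Low to an alert on the same side | 4 | No |
| Level 1 to Level 2 on the same side | 2 | No |
| Total | 12 | 6 yes, 6 no |

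**Step 3: reaching an alert from a non-alert baseline on the same side.** There are 4 + 4 = 8 such transitions. Four are unseen and four are seen without their alert level, so none of the 8 can be read as an alert from the table.

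**Step 4: opposite-direction moves.** A change such as Low to High Level 2 appears as Low to High. It registers, again without its alert level.

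**Step 5: other routes to a frequency.**

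- *Adverse events.* Under protocol 8.1.1 a laboratory abnormality that the investigator judges clinically significant is an adverse event, except where it is associated with the underlying disease and no more severe than expected. Adverse events are graded by CTCAE (protocol 8.2.1.1), and SAP 11.11.1 tabulates them by preferred term and by worst grade. This gives a frequency with a degree, but entry depends on investigator judgment and coding.
- *Minimum and maximum by visit.* These show the largest excursion at each visit, but not how many subjects had one.
- *Listings.* These hold the full indicators subject by subject. A frequency could be counted from them by hand, but none is planned in the text.
- *Unscheduled values.* Protocol 6.3.4 asks for clinically significantly abnormal tests to be repeated, and protocol 7.6 allows laboratory tests at unscheduled visits. SAP 10.5 keeps unscheduled visits out of the table summaries, so a value taken there reaches listings only.

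**Step 6: comparison with the protocol.** Protocol 10.4.3 plans frequency tables, and shift tables where applicable, for categorical safety data. SAP 11.11.3 provides shift tables and names no frequency table of marked abnormalities. SAP 12, which records changes from the protocol, does not mention this.

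**The case against.** The strongest reply is that little is lost. The grading is dropped only in the shift tables; listings keep it, and separate listings pick out the markedly abnormal subjects. Half of the same-direction worsening transitions still register, including every move from Normal, and so do all opposite-direction moves. Adverse event tables show degree through CTCAE grade, and by-visit minima and maxima show the extremes. All of that stands, and it limits the point to a missing count and to worsening from an already abnormal baseline.

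Three stronger readings are tempting, and the documents do not support them.

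- **That the named endpoint goes unreported.** The endpoint concerns clinically significant results. In its adverse event definition the protocol leaves that judgment to the investigator, and those results do enter the adverse event tables, with grade.
- **That an alert is a clinically significant result.** The documents give no thresholds for Level 1 or Level 2 and attach no clinical meaning to them. A count of alerts would complement the endpoint; it would not be the endpoint.
- **That many subjects are affected.** The documents hold no laboratory data. Applying an assumed rate of baseline abnormality to the planned 850 subjects would count those who start abnormal, not those who worsen.

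The outline of tables in SAP section 15 has no content in the text available, so a count table specified there cannot be ruled out. If there is one, SAP 11.11.3 should refer to it.

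**Conclusion.** The point holds in a limited form. Under the SAP's mapping, 6 of 12 same-direction worsening transitions cannot appear as shifts, and the 4 transitions from Normal to an alert cannot be told apart from milder ones. Marked laboratory abnormalities are listed without a stated criterion and without a count, although the same plan both defines and counts them for blood pressure and pulse. The endpoint on clinically significant results therefore rests on investigator-judged adverse events, by-visit extremes and listings, with no objective laboratory frequency beside them.

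The 6 of 12 describes the table's structure, not the share of subjects affected. The conclusion assumes that the text of SAP 11.11.3 is a full account of the laboratory tables. No efficacy result is affected. The change is worth making because it supports a named safety endpoint with indicators that already arrive from the laboratory.

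**What to change.** In SAP 11.11.3:

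1. Keep the three-level shift tables. Seven levels would give 7 × 7 = 49 cells in place of 3 × 3 = 9, which is a matter of preference and is not needed to answer the endpoint.
2. Add one table, by analyte, for each pivotal-study treatment group and overall: n (%) of subjects whose worst post-baseline value reaches a Level 1 or a Level 2 alert, low and high separately, with the baseline level shown. Use as denominator the subjects with at least one post-baseline result for that analyte.
3. State that values from unscheduled visits count in this table, as an exception to SAP 10.5.
4. State the criterion for a markedly abnormal laboratory value, as SAP 11.11.4 does for vital signs.
5. Describe alert level as an objective complement to investigator-judged clinical significance, not a synonym for it.

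The cost is one additional table and its programming. No new data are collected.
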